[name] will recruit from local early intervention providers (including Birth to Three Developmental Services, A Step Ahead in Pierce County, and Tacoma Learning Center), Mary Bridge Children's Hospital, the Children's Therapy Unit, and from Washington Pediatric Special Interest Group. [name] has successfully recruited subjects from these sites previously.

No problems with recruitment of study participants are anticipated due to each investigator's connections in their local medical community. If one of the sites should fall short of qualified children, more children could be covered at one of the other sites. Drop-out rates are expected to be low due to the home-based nature of the study. All of the outcome measures as well as the intervention will be conducted at the children's homes. It is possible that a young child might fall sick for any of the planned visits by the PIs, or might not fully participate in one of the visits for other reasons. In this event, the PI will reschedule a repeat visit within a few days of the original visit to collect the data.

Between the three sites, twelve children will receive high-intensity treadmill training and twelve children will receive low-intensity treadmill training. Due to the stringent inclusion and exclusion criteria, the children in the two groups are expected to show no significant between-group differences at baseline. In [name] previous study on home-based treadmill training, group allocation using the same criteria led to two groups with no significant differences regarding age and developmental skills.¹⁷

Power Analysis

Power analysis was conducted to determine a sample size based on developmental data and based on StepWatch data.

To examine the optimal dosing for walking attainment, a projected sample size of 18 subjects (9 per group) at 95% power was calculated from Peabody Developmental Motor Scales-2 Locomotion subscale change scores from [name] previous home-based treadmill training study (n=12; GMFCS levels I and II; ages 15-32 months)¹⁷. An additional 6 subjects will be added to strengthen the study design and allow for possible attrition, leading to a total number of 24 subjects.

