To assure sufficient power to assess the effects of treadmill training on overall walking activity, a proposed sample size of 12 per group would have 80% power to detect a 3000 stride/day difference in treatment intensity as measured with the StepWatch monitor. This is based on [name] cross-sectional StepWatch average stride/day data from 17 youth with CP ages 2-3 years where the mean difference between GMFCS level I and II was 3000 strides.¹⁸

[figure not shown]

Fig. 4. Power analysis for sample size ($\alpha = 0.0$; Power= 0.95; Effect size=1.87; Sample size=18)

Methodology

Approval from the University Institutional Review Board was submitted on July 10, 2014 and approved on July 29, 2014 by the lead institution at California State University, Sacramento. A cooperative agreement will be put in place prior to study onset with the other institutions (please see attached). Due to the children's young age, written informed consent will be obtained from the parents. Parents will be asked to commit to a 6-week stretch uninterrupted by vacations or breaks. Study participation will be discussed and scheduled carefully with the families to allow for 6 weeks of uninterrupted intervention period. Due to the nature of the home-based administration of the intervention by parents and caregivers, high adherence to the study protocol is expected. Investigators will schedule weekly home visits and all assessments at a mutually agreed upon time that is convenient for the families.

After consenting to study participation, the parents for each child will fill out a parent questionnaire containing demographic and health information about their child. A physician form will also be signed prior to study onset to seek medical clearance for the child for the intervention. Group allocation will be determined by blinded drawing from a hat until each of the three study sites has reached a total of 4 children in each group. In the unlikely event that one site might have difficulty with subject recruitment, additional children will be enrolled at another study site.

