Each child will be tested at pre-intervention, post-intervention, at 1-month and at 4-months following the intervention. The testing will be scheduled at a mutually agreed-upon and convenient time with the family at their home. The children will undergo 6 weeks of treadmill training in their homes administered by a parent or primary caregiver who has been trained to safely provide the intervention. Weekly visits will be conducted by the researchers to adjust the treadmill speed and make any needed corrections to the parents' technique. The treadmill speed will be increased each week as tolerated by the child. The speed will not exceed 0.6 meter/second. In a previous study by [name] using a similar sample and treadmill protocol, the average starting speed was 0.1 meters/second and increased to an average of 0.25 meter/second over the duration of 6 weeks.¹⁷ Children assigned to the high-intensity group will walk on the treadmill 5 days/week, twice daily for 10-20 min for 6 weeks. Children in the low-intensity group will walk on the treadmill 2 days/week, once daily for 10-20 minutes for 6 weeks. The children will be motivated during the treadmill walk with a child-friendly video shown on a television, computer, or tablet. If uninterested, children will be encouraged with other motivational toys suggested by the parents. These motivational methods led to high adherence in [name] previous study on a similar sample of young children with CP.¹⁷

There is a possibility that a child might miss a training session due to sickness or other family obligations. The parents will be encouraged to make up a missed session on a different day. In the low-intensity group, the children have 5 days/week without treadmill training that could be used as make-up days. In the high-intensity group, the children have 2 days/week without treadmill training that could be used as make-up days. If a missed day cannot be made up, the parents will be encouraged to attempt to

train for the maximal 20 minutes for each treadmill walk in order to make up some of the missed minutes during other walks. The parents will document the minutes walked and the speed of each treadmill walk on a paper flow chart that is provided to them by the PIs.

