Outcome measures at the *activity level* of the International Classification of Functioning, Disability and Health (ICF) Model will include the Gross Motor Function Measure (GMFM), Peabody Developmental Motor Scales-2 (PDMS-2), Functional Mobility Scale (FMS), the Timed 10-meter Walk Test, the 1-minute Walk Test and the StepWatch accelerometer. Outcome measures at the *participation level* of the ICF Model will be the Pediatric Evaluation of Disability Inventory Caregiver Mobility Scale (PEDI). Videotapes of assessments will be scored by an assessor blinded to group allocation for the GMFM and PDMS-2. StepWatch data will be collected for all awake daytime hours over a 7 day period at study onset before treadmill training commences and at each of the post-intervention assessments. The StepWatch monitor will be secured around the child's ankle with a small knit cuff. [name] has successfully employed this method of monitor attachment in toddlers with and without motor limitations.^{23,36} StepWatch outcomes will be average number of strides/day and the percentage of the time walking.

[figure not shown]
In order to address specific aim # 1 (optimal parameters for dosing home-based treadmill training by comparing high-intensity to low-intensity treadmill training) and specific aim # 2 (effects of high- versus low-intensity treadmill training on walking attainment and overall walking activity), between-group differences of all the outcome measures will be analyzed as described in the next section. Specifically, between-group differences in GMFM and PDMS-2 will examine the effects of dosage on walking attainment and skills related to standing and walking. The changes in support needed for walking will be measured by the FMS in the two groups. Differences in walking speed and walking endurance will be analyzed using the data from the Timed 10-meter Walk Test and the 1-minute Walk Test, respectively. The parent perspective on overall child mobility will be analyzed by using the PEDI. Finally, overall walking activity will be shown by between-group differences from the StepWatch data.

Data Analysis

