A one-way analysis of variance (ANOVA) with repeated measures will be used for comparison of treatment groups for parametric dependent variables, i.e. PDMS-2, GMFM, Timed 10-meter Walk Test, and 1-minute Walk Test. Analysis for non-parametric data for dependent variables, i.e. PEDI and FMS, will be conducted using the Friedman test for comparison between groups. StepWatch data will be examined with the Wilcoxon sign rank test for paired data. Post hoc tests will be performed where appropriate. Alpha will be set at 0.05. In addition, data on whether children reached the minimum clinically important change will be reported for the GMFM.³⁷

[figure not shown]
Study Timeline

Overall Study Timeline

Study recruitment will commence as soon as all study sites have signed the cooperative IRB agreement. All equipment will be ordered immediately after the receipt of the grant. Training on StepWatch use will be conducted by [name] at Seattle Children's Research Institute. [name] and [name] will participate. During the same meeting, reliability training will be conducted on other outcome measures. Recruitment and enrollment will commence immediately by distributing study information at the three sites. It is anticipated that there will be coinciding intervention and data collection for the 8 children at each site for the duration of 15 months. Two treadmills will be available at each site for the 6-week treadmill intervention periods for each child. Video review will be ongoing by the consultant, who is blinded to group allocation, as the videos become available for each child. Preliminary data analysis will be conducted in order to present initial results at conference within the grant period. Once all data is collected, there will be a second on-site meeting of the three PIs in order to assure consistent data entry and to allocate the responsibilities for study result dissemination. All three investigators will engage in manuscript preparation with [name] as first author. Data analysis will be performed by a statistician at the lead institution in collaboration with the PIs. Manuscript preparation will be conducted in the final two months of the 24-month study period.

Study Timeline for Each Subject

As indicated above, each child will be enrolled in the study for a total period of 26 weeks.

Human Subjects

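### The one-way repeated-measures ANOVA in the Data Analysis section is not the PDMS-2 Locomotion change-score comparison that sized the trial, and the deciding contrast is not named

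*Combined protocol and SAP*

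**What the plan says.** The Data Analysis section is the only place where the test is specified: "A one-way analysis of variance (ANOVA) with repeated measures will be used for comparison of treatment groups". It applies this to PDMS-2, GMFM and the 10-meter and 1-minute walk tests. It then adds: "Post hoc tests will be performed where appropriate".

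The visit schedule, in Outcome Measures and again in Methodology, has four assessments, one of them before treatment: "Each child will be tested at pre-intervention, post-intervention, at 1-month and at 4-months following the intervention". Methodology says that "between-group differences in GMFM and PDMS-2 will examine the effects of dosage on walking attainment" and refers to the Data Analysis section for the method.

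The Power Analysis section sizes the trial on a different quantity: "a projected sample size of 18 subjects (9 per group) at 95% power was calculated from Peabody Developmental Motor Scales-2 Locomotion subscale change scores", taken from an earlier home-based treadmill study. The caption of the power figure gives "Power= 0.95; Effect size=1.87; Sample size=18". Six further children bring the total to 24, or 12 per arm.

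On baseline, the Enrollment procedures section says only that "the children in the two groups are expected to show no significant between-group differences at baseline". Nowhere do the documents name a group-by-visit term, a change-score contrast, a baseline covariate or a deciding visit for these outcomes.

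**The concern.** A change score removes each child's own starting level. The ANOVA as worded does not clearly do so. The word one-way allows a single factor, and neither choice gives the comparison that was sized:

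- **Factor is visit.** The test asks whether scores change over time in all children together. It does not compare the arms.
- **Factor is group.** The test compares the arms on the mean of four visits. The randomised arms are expected to be equal at the pre-treatment visit, so including it dilutes the difference. The between-child variance also stays in the error term.

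A two-factor analysis with a group-by-visit interaction would be close to the sized comparison, but the plan does not say so. The statistician would have to choose among tests that can disagree on the same 24 children. The Study Timeline also foresees a preliminary analysis for a conference, so the choice could be made after results have been seen.

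**Working it through.** **Inputs from the documents.** Effect size 1.87, power 0.95, 9 per group (Power Analysis and figure caption); 12 per arm enrolled (Enrollment procedures); four visits, one before treatment (Methodology); alpha 0.05 (Data Analysis).

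**Assumptions.** Two-sided test; 1.87 is a standardised mean difference on the change score; equal variances; the same correlation ρ between any two visits (not in the documents, so ranged); no true baseline difference; no dropout.

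**1. The plan's own figure.** Two-sample t-test on change scores, noncentrality 1.87 × √(n/2), 2n − 2 df.
- n = 8: 3.74, power 93.5%
- n = 9: 3.97, power 96.1%
- n = 12: 4.58, power 99.2%

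Nine per group is the smallest size that reaches 95%, so the stated figure reproduces.

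**2. Group main effect over four visits, sustained effect.** In units of the raw SD, a change score has SD √(2(1 − ρ)), so the arm difference at each later visit is δ = 1.87 × √(2(1 − ρ)). The four-visit mean difference is (0 + δ + δ + δ)/4 = 0.75δ. A child's four-visit mean has variance (1 + 3ρ)/4. Noncentrality = 0.75δ / √[(1 + 3ρ)/4 × 2/n], 2n − 2 df.

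Example, ρ = 0.7 and n = 12: δ = 1.87 × √0.6 = 1.448; 0.75δ = 1.086; standard error √(0.775 × 2/12) = 0.359; noncentrality 3.02 on 22 df; power 82.3%.

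| ρ | δ | 9 per arm | 12 per arm |
|---|---|---|---|
| 0.4 | 2.05 | 98.5% | 99.8% |
| 0.5 | 1.87 | 94.2% | 98.6% |
| 0.6 | 1.67 | 84.7% | 93.9% |
| 0.7 | 1.45 | 69.1% | 82.3% |
| 0.8 | 1.18 | 48.3% | 61.5% |
| 0.9 | 0.84 | 25.6% | 33.3% |

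Power falls below 95% once ρ exceeds about 0.49 with 9 per arm or 0.58 with 12. A simulation of 40,000 trials per cell with 12 per arm gave 98.7%, 82.2%, 61.7% and 33.4% at ρ = 0.5, 0.7, 0.8 and 0.9.

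The main effect matches the change score where 0.75 × √(2(1 − ρ)) = √((1 + 3ρ)/4). This gives 1.125(1 − ρ) = 0.25 + 0.75ρ, so ρ = 0.875/1.875 = 0.47. Below that value the main effect is the stronger of the two.

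**3. Group-by-visit, same effect.** Noncentrality λ = (n/2) × Σ(δₜ − mean)²/(1 − ρ). For the pattern 0, 1, 1, 1 the sum is 0.75δ², and ρ cancels: λ = n × 0.75 × 1.87² = 31.5 for n = 12 (F on 3 and 66 df, power 99.8%) and 23.6 for n = 9 (3 and 48 df, 98.4%).

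**4. Baseline-adjusted post-intervention comparison.** Noncentrality = δ / √[(1 − ρ²) × (2/n) × (1 + 1/(2n − 4))], 2n − 3 df. With 12 per arm, power is at least 99% for ρ from 0.4 to 0.9.

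**5. Fading effect (1, 1/2, 0 of δ at the three later visits).** The four-visit mean difference is 0.375δ. With 12 per arm the main effect has 68% power at ρ = 0.4, 55% at 0.5 and 30% at 0.7.

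**6. Correlation that decays with visit distance (AR(1)), sustained effect, 12 per arm.** At adjacent-visit correlations 0.7, 0.8 and 0.9, simulated main-effect power is 87%, 66% and 34%. Group-by-visit with a Greenhouse-Geisser correction has about 95%, 93% and 91%. Without the correction its type I error rises above 6%, so the correction is needed.

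**The case against.** The strongest reply is that one-way is a slip. The phrase about comparing treatment groups, set beside four visits, fits a mislabelled group-by-visit ANOVA equally well, and on that reading power is kept: 98.4% with 9 per arm and 99.8% with 12. This stands in so far as the defect lies in the specification; no power loss is demonstrated. But that reading cannot be assumed. The neighbouring sentences assign a Friedman test to a comparison between groups and a paired signed-rank test to StepWatch. Both are within-subject procedures, so the section does not reliably describe a two-arm longitudinal comparison.

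Second, the loss depends on a correlation that the documents do not give. This also stands. At 0.4 with 12 per arm, main effect and group-by-visit both have 99.8% for a sustained effect at the design value. For a smaller sustained effect of 0.8 raw SD the ranking reverses at 0.4: 47% for the main effect against 40% for group-by-visit.

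Third, an unadjusted comparison of randomised arms is valid. That is correct: the issue is power and an open choice of test, not bias.

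A reader might infer that GMFM also falls short of 95% power. The documents do not support this. Effect size and power are stated only for PDMS-2 Locomotion. For GMFM and the two walk tests, only the structural point applies.

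**Conclusion.** The point holds as a mismatch between the analysis and the sample-size calculation. Neither literal reading of the ANOVA is the change-score comparison that was sized: one does not compare the arms, and the other averages in the pre-treatment visit. The test that would come close is not named, and neither is a deciding visit.

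The size is conditional. With 12 per arm and a sustained effect at the design value, the main-effect reading misses 95% only if the between-visit correlation exceeds about 0.58; it then falls to 82.3% at 0.7 and 33.3% at 0.9. A fading effect lowers it at every correlation, to 68% already at 0.4.

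A reader might infer that the trial is too small, or that it will lose power. Neither follows. The stated 9 per group reproduces, and at the design effect 24 children are ample for a test that uses the pre-treatment score as a baseline. The change should be made, but it is one of wording. My confidence is medium, because the correlation and the intended reading are both unknown.

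**What to change.** For PDMS-2 and GMFM-66, replace the one-way ANOVA with one linear mixed model of the post-intervention, 1-month and 4-month scores on arm, visit, arm-by-visit and baseline score, with child as random effect. The pre-intervention score is then a covariate and not part of the tested mean. Before any data are seen, including for the preliminary conference analysis, name one deciding arm contrast per outcome. Report the adjusted arm difference with its 95% confidence interval at every visit.

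An acceptable minimum is to name the group-by-visit interaction, with a sphericity correction, and one deciding visit expressed as change from baseline.

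No new visits, children or data are needed, and the covariate costs one degree of freedom. The real cost is the risk of naming a contrast that does not fit the time course. With 12 per arm, the design effect and ρ from 0.5 to 0.9 (baseline-adjusted formulas, with residual variance (1 + 2ρ)/3 − ρ² for the follow-up mean):

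| Time course of the effect | Post-intervention visit | Mean of three follow-ups | Group-by-visit |
|---|---|---|---|
| Builds slowly (1/3, 2/3, 1) | 31–38% | 95–99% | 98.5% |
| Gone by 4 months (1, 1/2, 0) | at least 99% | 78–91% | 99.6% |

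Group-by-visit keeps at least 98.5% in the time courses examined, under equal correlation. It does not say at which visit the arms differ, which is why the minimum version also needs a deciding visit. The sponsor should choose the contrast from the time course it expects.

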The study protocol was submitted to the Institutional Review Board (IRB) at California State University, Sacramento, on July 10, 2014 and approved on July 29, 2014 (IRB protocol #13-14-156). In addition, the consent form, permission to be videotaped, parent questionnaire and physician form for the study were all approved by the IRB. Once the grant is received, a cooperative agreement form will be signed by the two participating universities before the study commences.

Selection of the families will be made by judgment of the PI. Factors will include parental ability to correctly perform the treadmill training and safety during treadmill training sessions. The PIs reserve the right to terminate participation in the study if parents are unable to adhere to the agreed-upon treatment regimen, or display incorrect or unsafe technique during training. Any adverse events will be reported to the IRB. Because this intervention is conventionally used in physical therapy practice, adverse events are not anticipated. A small incentive will be offered to families to encourage participation. The families have the right to terminate participation in the study without any reason or penalty.

The study will be conducted in the children's homes. The last names of the children will not be used when other persons are present in the area. The PIs will abide by Health Insurance Portability and Accountability Act (HIPAA) regulations on children's privacy. When reporting results, only ages, diagnosis, functional level and gender of children will be reported. Photographs and/or video clips of children might be used when reporting results, but only with written permission of the parents/guardians. No mention of exact geographical location will be made.

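### The repeated-measures ANOVA planned for PDMS-2 and GMFM would, on its natural reading, drop a child who withdraws after the post-intervention test, and nothing in the plan provides otherwise

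*Combined protocol and SAP*

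**What the plan says.** The Data Analysis section gives one method for PDMS-2 and GMFM: "A one-way analysis of variance (ANOVA) with repeated measures will be used for comparison of treatment groups for parametric dependent variables". It adds "Alpha will be set at 0.05", post hoc tests where suitable, and a report of which children reached the minimum important change on the GMFM.

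The schedule appears under both Outcome Measures and Methodology: "Each child will be tested at pre-intervention, post-intervention, at 1-month and at 4-months following the intervention". The timeline for each subject says that "each child will be enrolled in the study for a total period of 26 weeks", of which six weeks are treadmill training.

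The documents touch on losses in four places:
- Human Subjects: "The families have the right to terminate participation in the study without any reason or penalty".
- Power Analysis: "An additional 6 subjects will be added to strengthen the study design and allow for possible attrition", which takes the total from 18 to 24.
- Enrollment procedures: dropout is expected to be low because the study is home-based, and a visit missed through illness or poor cooperation is rescheduled within days.
- Methodology: the data of a child removed because the parent cannot train safely are excluded.

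The documents contain no mixed model, imputation, analysis population or general rule for missing data.

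**The concern.** A classical repeated-measures ANOVA needs a value at every level of the within-child factor. A child who trains for six weeks, is scored at post-intervention and then leaves before the 1-month or 4-month visit has an incomplete row, and the method drops the whole row. The post-intervention score is valid and already held, but that analysis does not use it.

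Two things are at stake. The first is precision, in a trial of 12 children per arm. The second is bias: the post-intervention comparison would depend on who stayed for four further months. If staying depends on both arm and gain, the completers in the two arms are no longer comparable, even though the gains that predict leaving were observed. The PDMS-2 and GMFM comparisons carry the question of dose and walking attainment, and PDMS-2 Locomotion change is a basis of the sample size.

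**Working it through.** **1. The plan's own figure.** Power Analysis states that "a projected sample size of 18 subjects (9 per group) at 95% power was calculated from Peabody Developmental Motor Scales-2 Locomotion subscale change scores", and the figure caption gives "Power= 0.95; Effect size=1.87; Sample size=18". Inputs: standardised effect d = 1.87 and alpha 0.05 from Data Analysis, taken as two-sided because sidedness is not stated. For a two-sample t-test with n per arm, the noncentrality is d × √(n/2) on 2n − 2 degrees of freedom. Power is 93.5% at n = 8 and 96.1% at n = 9, so 9 per arm is the smallest size reaching 95%. The total of 18 reproduces, as a two-group comparison of change scores.

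**2. What the method does with an incomplete child.** I simulated 24 children at four visits and removed only the 4-month value from four of them. A standard repeated-measures ANOVA routine rejected the data as unbalanced. Restricting to complete children used 20 of the 24 observed post-intervention scores. A mixed model used all 24 children and 92 observations (24 × 4 − 4).

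**3. Precision and power.** With n rather than 12 per arm and the same SD, the standard error is multiplied by √[(2/n)/(2/12)] = √(12/n). The number lost is an assumption; three per arm uses up the whole six-child addition. The effect of 1.2 is also assumed.

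| Lost per arm after post-intervention | n per arm | SE multiplier | Power at d = 1.87 | Power at d = 1.2 |
|---|---|---|---|---|
| 0 | 12 | 1.000 | 99.2% | 80.2% |
| 1 | 11 | √(12/11) = 1.044 | 98.6% | 76.3% |
| 2 | 10 | √(12/10) = 1.095 | 97.7% | 71.8% |
| 3 | 9 | √(12/9) = 1.155 | 96.1% | 66.7% |

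**4. Bias.** All inputs here are assumed. Let z be a child's gain within its arm, in SD units, with logit P(leave) = a − z: children who gain less leave more often, with slope 1 per SD. The constant a is set in each arm to give the chosen dropout rate. The mean of z among those who stay is E[z × P(stay)] / E[P(stay)] over a standard normal z:
- 35% dropout: a = −0.746, mean among stayers +0.292.
- 15% dropout: a = −2.048, mean among stayers +0.133.

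The completer difference is the true difference plus the high-arm shift minus the low-arm shift. With a true difference of 1.00 SD:
- 35% high arm, 15% low arm: 1.00 + 0.292 − 0.133 = 1.16.
- 15% high arm, 35% low arm: 1.00 + 0.133 − 0.292 = 0.84.
- Equal dropout: the shifts cancel and the result is 1.00.

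For scale, the standard error of the difference at 12 versus 12 is √(2/12) = 0.41 SD, so a bias of 0.16 SD is about 0.4 of a standard error.

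**The case against.** The strongest reply is that the central step is inferred. Data Analysis does not say that all four visits enter one model, or that incomplete children are deleted; the visit schedule is not a model statement. That is right, and the point is therefore conditional on the natural reading. The silence does not help the plan, though: if something else was intended, it would be chosen after the data are in.

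A reader might infer that such a child disappears from every analysis. The documents do not support that. The post hoc tests and the GMFM minimum-important-change report could still use the post-intervention score, although the plan does not commit either to doing so.

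A reader might also infer that the trial's primary contrast is lost. No visit is named as primary, and a literal one-way repeated-measures ANOVA has no between-group factor. How the arms are compared is a wider gap in the same sentence, and the model proposed here would also close it.

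Third, the losses may be small. Dropout is expected to be low, visits are at home, families receive an incentive, and the six extra children cover the numbers at the planning effect. This stands as regards power. The extra children do not correct selective loss, and rescheduling does not reach a family that has left. The rule excluding data after unsafe technique concerns a different group and should not be read as a rule for voluntary withdrawal.

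Last, the bias figures rest on chosen dropout rates and a chosen slope. They do, which is why both directions and the null case are shown.

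**Conclusion.** The point holds in conditional form. If all visits enter one classical repeated-measures ANOVA, a child who withdraws between the post-intervention and 4-month visits is lost from the PDMS-2 and GMFM analysis together with a valid post-intervention score, and no statement in the documents prevents this.

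The size depends on late dropout that the documents do not quantify. One to three children lost per arm cost 4% to 15% in standard error. Power at 1.87 is not threatened, so a reader should not conclude that the trial becomes underpowered on its own planning assumption; power suffers materially only if the true effect is smaller, for example 80% falling to 67% at an assumed 1.2. Nor should a reader conclude that the analysis is tilted towards high intensity. Bias needs dropout related to both arm and gain, its direction cannot be known in advance, and the 1.16 and 0.84 are illustrations rather than predictions. The change is still worth making, because a better method is available at almost no cost.

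**What to change.** In Data Analysis, replace the repeated-measures ANOVA for PDMS-2 and GMFM with a linear mixed model for the post-intervention, 1-month and 4-month scores. Specify arm, visit and arm-by-visit as fixed effects, the pre-intervention score as covariate, correlation within child, and a small-sample degrees-of-freedom correction such as Kenward-Roger. Include every child with at least one post-baseline score. Report the high-versus-low contrast at each visit and the number analysed by arm and visit.

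The cost is a change of wording and slightly more work for the statistician already planned; no child, visit or measurement is added. The model relies on data being missing at random given the observed scores, and the plan should say so. The covariate and the degrees-of-freedom correction are good practice in a trial this small. The essential part is that all observed post-baseline scores are used.
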